### **6.2.2. Day 1 Assessments**

The following evaluations are to be completed at the Day 1 Visit. **The Investigator must have confirmed eligibility before proceeding with the Day 1 visit.** The subject must complete all study procedures before being administered the study drug:

- Review of AEs and changes in concomitant medications
- Complete physical examination (urogenital/anorectal exams will be performed at the discretion of the Investigator)
- Vital signs measurement (blood pressure, pulse, respiration rate, and temperature), including weight
- 12-lead ECG performed supine
- Urine collection for the following laboratory procedures:
  - Urinalysis
  - Urine albumin, urine creatinine, urine protein, retinol binding protein and beta-2 microglobulin
  - Urine pregnancy test (women of childbearing potential only); positive urine pregnancy tests will be confirmed with a serum test. If the test is positive, the subject will not be able to participate.
  - Urine storage sample for possible additional clinical testing

- Blood sample collection for the following laboratory analyses:
  - Chemistry profile: alkaline phosphatase, AST, ALT, GGT, total bilirubin, direct and indirect bilirubin, total protein, albumin, bicarbonate, BUN, calcium, chloride, creatinine, phosphorus, magnesium, potassium, sodium, uric acid, and amylase (reflex lipase testing is performed in subjects with total amylase  $> 1.5 \times \text{ULN}$ ), and TSH, PT/INR (prothrombin time/international normalized ratio)
  - Metabolic assessments: Fasting (no food or drinks, except water, at least 8 hours prior to blood collection) glucose and lipid panel (total cholesterol, HDL, direct LDL, and triglycerides). If the subject has not fasted prior to the visit, the visit may proceed, but the subject must return within 72 hours in a fasted state to draw blood for the metabolic assessments.
  - Estimated glomerular filtration rate according to the Cockcroft-Gault formula
  - Hematology profile: complete blood count (CBC) with differential and platelet count
  - Plasma HIV-1 RNA
  - CD4+ cell count
  - Plasma storage samples for safety, virology, or PK testing
  - Whole blood sample for potential virologic resistance testing and/or HIV DNA genotyping
  - Subjects who meet the definition of HBV infection at Screening Visit (positive serum HBsAg or positive HBcAb with quantifiable HBV DNA), will have plasma HBV DNA tested
- PPD
- P
- Provide subject dosing diary to all subjects in Treatment Group 1

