- Dispense study drug
- Subjects in treatment group 1 should be instructed to take study drugs without regard to food. Subjects in treatment group 2 should be instructed to take study drug with food. Subjects are required to initiate dosing of study drugs the day of the Day 1 visit. The subject should be counseled regarding the importance of adherence and taking their study medications at approximately the same time each day as directed by the Investigator.

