### **8.6.3.        Laboratory Evaluations**

Selected laboratory data (using conventional units) will be summarized using only observed data. Absolute values and changes from baseline at all scheduled visits will be summarized.

Graded laboratory abnormalities will be defined using the grading scheme defined in Grading of laboratory abnormalities attached in [Appendix 4](#).

Incidence of treatment-emergent laboratory abnormalities, defined as values that increase at least 1 toxicity grade from baseline at any time post baseline up to and including the date of last dose of study drug plus 30 days, will be summarized by treatment. If baseline data are missing, then any graded abnormality (i.e., at least a Grade 1) will be considered treatment emergent. The maximum post baseline toxicity grade will be summarized by laboratory parameter.

Laboratory abnormalities that occur before the first dose of study drug or after the last dose of study drug plus 30 days will be included in a data listing.

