3.8.1. Definitions

Study Day 1 is defined as the day when the first dose of B/F/TAF (either in the randomized phase or extension phase) was taken. For subjects randomized to the B/F/TAF group, the first dose date is the same as the randomized phase first dose date. For subjects randomized to the SBR group, the first dose date is defined as the earliest nonmissing start date of B/F/TAF recorded on the Study Drug Administration eCRF.

Study Days are calculated relative to Study Day 1 for the all B/F/TAF analysis. For events that occur on or after the Study Day 1 date, study days are calculated as (visit date minus date of the first dose plus 1). For events that occur prior to Study Day 1, study days are calculated as (visit date minus date of the first dose).

Last Dose Date is defined as the maximum, nonmissing end date of B/F/TAF, recorded on the Study Drug Administration eCRF form with “Study Drug Permanently Discontinued” box checked for subjects who prematurely discontinued study drug or who completed study drug according to the Study Drug Completion eCRF.

If the date of last dose is missing (eg, due to lost to follow-up) for subjects who prematurely discontinued study drug, the maximum of nonmissing study drug start dates and end dates, the clinical visit dates, and the laboratory visit dates excluding the date of 30-day follow-up visit will be used to impute the last dose date.

Last Study Date is the maximum of nonmissing study drug start dates and end dates, the clinic visit dates, and the laboratory visit dates, including the 30-day follow-up visit date for subjects who prematurely discontinued or completed the study according to the Study Completion eCRF.

Baseline value is defined as the last nonmissing value obtained on or prior to the Study Day 1 for all assessments.

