3.8.2. Analysis Windows

Subject visits might not occur on protocol-specified days. Therefore, for the purpose of analysis, observations will be assigned to analysis window. Since the final analysis only includes the all B/F/TAF analysis, only data included in the all B/F/TAF analysis will be assigned analysis windows.

For data listings, the observations collected from the randomized phase of the study for the subjects who were randomized to SBR group will not have analysis window assigned and will be included in listings with derived visit as blank.

The analysis windows for HIV-1 RNA, CD4+ cell count, CD4 %, hematology, chemistry, urinalysis, urine pregnancy laboratory tests, eGFR_{CG}, vital signs, and weight are presented in [Table 3-1](#).

Table 3-1. Analysis Windows for HIV-1 RNA, CD4+ cell count, CD4 %, Hematology, Chemistry, Urinalysis, and Urine Pregnancy Laboratory Tests, eGFR_{CG}, Vital Signs, and Weight

Visit ID	B/F/TAF			SBR to B/F/TAF		
	Nominal Day	Lower Limit	Upper Limit	Nominal Day	Lower Limit	Upper Limit
Baseline			1			1
Week 4	28	2	42			
Week 8	56	43	70			
Week 12	84	71	126	84	2	126
Week 24	168	127	210	168	127	210
Week 36	252	211	294	252	211	294
Week 48	336	295	378	336	295	378
Week 60	420	379	462	420	379	462
Week 72	504	463	546	504	463	546
Week 84	588	547	630	588	547	630
Week 96	672	631	714	672	631	714
Week k	k*7	(k-6)*7+1	(k+6)*7	k*7	(k-6)*7+1	(k+6)*7

The analysis windows for metabolic assessments (including fasting glucose and lipid panel: total cholesterol, high density lipoprotein [HDL], direct low density lipoprotein [LDL], triglycerides, and total cholesterol to HDL ratio) are presented in [Table 3-2](#).

Table 3-2. Analysis Windows for Metabolic Assessments

Visit ID	B/F/TAF			SBR to B/F/TAF		
	Nominal Day	Lower Limit	Upper Limit	Nominal Day	Lower Limit	Upper Limit
Baseline			1			1
Week 12	84	2	126			
Week 24	168	127	252	168	2	252
Week 48	336	253	420	336	253	420
Week 72	504	421	588	504	421	588
Week 96	672	589	756	672	589	756
Week k	k*7	(k-12)*7+1	(k+12)*7	k*7	(k-12)*7+1	(k+12)*7

The analysis windows for thyroid stimulating hormone (TSH; thyrotropin) and renal function (including urine albumin, urine creatinine, urine RBP, and urine beta-2 microglobulin, and derived ratios assessments) are presented in [Table 3-3](#).

Table 3-3. Analysis Windows for TSH, Renal Function, and HCV RNA Assessments

Visit ID	Nominal Day	Lower Limit	Upper Limit
Baseline			1
Week 24	168	2	252
Week 48	336	253	420
Week 72	504	421	588

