7.2.2.1. Treatment Emergent Laboratory Abnormalities

Treatment-emergent laboratory abnormalities are defined as values that increase at least 1 toxicity grade from baseline at any postbaseline time point, up to 30 days from the last dose date of B/F/TAF. If the relevant baseline laboratory value is missing, any abnormality of at least Grade 1 observed within the time frame specified above will be considered treatment-emergent.

Fasting glucose and nonfasting glucose (including glucose results without a known fasting status) are graded based on different grading scales as specified in the protocol.

Treatment-emergent laboratory abnormalities will be summarized for fasting glucose. Maximum postbaseline grade, instead of treatment-emergent grade, for nonfasting glucose (including glucose results without a known fasting status) will be summarized, as nonfasting glucose was not assessed at baseline visit for most of the subjects; therefore, an abnormality is treatment-emergent or not cannot be determined for these subjects.

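### Women randomised to B/F/TAF whose fasting lipids and glucose are redrawn on Study Day 2-4 lose their fasting baseline, so pre-existing graded results are counted as treatment-emergent

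*SAP*

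**What the plan says.** **Collection.** Fasting glucose and the lipid panel are first scheduled at Day 1. If the woman has not fasted, Protocol 6.2.2 says "the visit may proceed, but the subject must return within 72 hours in a fasted state to draw blood for the metabolic assessments". The same section says "Subjects are required to initiate dosing of study drugs the day of the Day 1 visit", and Protocol Appendix 2, footnote b, repeats same-day dosing. Section 6.2.2 also opens with "The subject must complete all study procedures before being administered the study drug". The Screening list in Protocol 6.2.1 has no lipid panel. It includes glucose, but without a fasting requirement.

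**Baseline.** SAP 3.8.1 sets Study Day 1 as the date of first B/F/TAF dose and adds "Baseline value is defined as the last nonmissing value obtained on or prior to the Study Day 1 for all assessments". SAP 3.8.3 and 7.2.1 repeat the cut-off. The table titled "Table 3-2. Analysis Windows for Metabolic Assessments" ends baseline at Day 1 and, for women randomised to B/F/TAF, runs the Week 12 window from Day 2 to Day 126.

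**Grading.** SAP 7.2.2 does not grade lipids that are nonfasting or of unknown fasting status. SAP 7.2.2.1 begins its rule "If the relevant baseline laboratory value is missing, any abnormality of at least Grade 1" and classes such a result, up to 30 days after the last dose, as treatment-emergent. Protocol 8.6.3 agrees: "If baseline data are missing, then any graded abnormality (i.e., at least a Grade 1) will be considered treatment emergent". Protocol 8.3 likewise treats a missing pre-treatment result as normal in the laboratory abnormality summary. SAP Appendix 5, item 7, counts every post-baseline graded result, whether or not it was selected for a by-visit table.

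Neither document makes an exception for the 72-hour redraw.

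**The concern.** Each rule is conventional on its own. Together they turn a sample that the protocol allows as the Day 1 metabolic draw into a post-baseline observation with nothing to compare it against. A stable raised cholesterol that the woman brought into the trial is then reported as emerging on B/F/TAF.

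Lipids are especially exposed. In Protocol Appendix 4, Grade 1 starts at 200 mg/dL for fasting total cholesterol and 130 mg/dL for fasting LDL. Lipids are also exempt from the convention that a value inside the reference range is Grade 0, so mild long-standing elevations do receive a grade.

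Safety and tolerability are the secondary objective, and the final analysis shows B/F/TAF exposure only. There is no concurrent control column in which a reader could notice that the count is inflated.

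**Working it through.** The plan states no figure on this point, so there is none to reproduce. The check is date logic followed by an illustration of size.

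**Step 1: where the redraw falls.** SAP 3.8.1 gives Study Day = (draw date - first-dose date) + 1. Dosing is on the day of the visit.

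| Hours from Day 1 visit | Study Day | Status under SAP 3.8.1 and Table 3-2 |
|---|---|---|
| 0, or 8 on the same date | 1 | Baseline |
| 24 | 2 | Week 12 window |
| 48 | 3 | Week 12 window |
| 72 | 4 | Week 12 window |

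The rule works by date, so a redraw later on the dosing day is still accepted. Only Days 2-4 are lost.

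**Step 2: can an earlier value stand in?**
- Lipids: none are taken at Screening, and a nonfasting Day 1 lipid result would not be graded. No trial sample qualifies.
- Glucose: SAP 7.2.2.1 puts fasting and nonfasting results on separate scales. A woman who happened to be fasted at Screening could have a usable value. Otherwise she has none.
- Parent-study values: the SAP does not say whether these may be used.

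**Step 3: the treatment-emergent flag.** With a baseline, the flag needs a post-baseline grade above the baseline grade. Without one, it needs any grade of 1 or more. For a woman whose grade never changes:

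| Stable grade | Fasted at Day 1 | Redrawn on Days 2-4 |
|---|---|---|
| 0 | Not flagged | Not flagged |
| 1, 2 or 3 | Not flagged | Flagged, possibly by the redraw itself |

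Fasting triglycerides have no Grade 1, so for that test the problem starts at Grade 2.

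**Step 4: by-visit tables.** SAP 3.8.3 picks the record closest to the nominal day, which is Day 84 for Week 12. A true Week 12 sample displaces the redraw. If no later fasting sample falls within Days 2-126, the redraw is tabulated as the Week 12 value. In either case she has no change score.

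**Step 5: illustrative size.** Let f be the share unfasted at Day 1 and redrawn on Days 2-4, and q the share of these with a stable pre-existing graded result on a given test. Neither is in the documents; both are assumed. The arm size of 235 is from SAP 1.3. Excess women = 235 × f × q; excess in percentage points = 100 × f × q.

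| f | q = 10% | q = 25% | q = 40% |
|---|---|---|---|
| 5% | 1.2 (0.5) | 2.9 (1.25) | 4.7 (2.0) |
| 10% | 2.4 (1.0) | 5.9 (2.5) | 9.4 (4.0) |
| 20% | 4.7 (2.0) | 11.8 (5.0) | 18.8 (8.0) |

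Cells show women, with percentage points in brackets. The ends are 235 × 0.05 × 0.10 = 1.2 and 235 × 0.20 × 0.40 = 18.8.

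**The case against.** The strongest reply is that the missing-baseline rule is deliberate. Protocol 8.3 and 8.6.3 pre-specify it, and it errs towards over-reporting abnormalities on the test drug. That is true, but it states the rule without curing its effect. SAP 7.2.2.1 itself takes a different course for nonfasting glucose: it drops the treatment-emergent classification because emergence cannot be judged without a baseline. A woman with no fasting baseline is in the same position.

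Other objections stand and limit the point:

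- **Size.** The unfasted share and the prevalence are assumptions. SAP 7.2.2.1 notes that most subjects had no nonfasting glucose at baseline, which suggests that unfasted women were a minority. Tables are by individual test, so cholesterol and LDL prevalence should not be pooled. A range based on any graded result also says nothing direct about the Grade 2-4 or Grade 3-4 tables.
- **Week 12 value.** The closest-day rule already handles this unless the later sample is also missing.
- **Standing.** Fasting metabolic results receive a short descriptive section (SAP 7.2.3), with no inference attached.

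A reader might infer two broader claims that the documents do not support. One is that the randomised Week 48 comparison is distorted. This SAP covers only the final all-B/F/TAF analysis. Protocol 8.6.3 carries the missing-baseline rule, but Protocol section 8 has no cut-off at first dose, and the Week 48 plan is not among the documents. The other is that SBR to B/F/TAF women are affected in the same way. They have scheduled fasting draws at Day 1 and Weeks 12, 24 and 48, and SAP 3.2 allows data up to the first extension dose to supply their baseline. The explicit same-day dosing instruction also concerns Day 1, not the start of the extension.

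**Conclusion.** The point holds for women randomised to B/F/TAF who are unfasted at Day 1 and redrawn on Study Day 2-4. Followed as written, the rules leave them without a fasting lipid baseline, and usually without a fasting glucose baseline. They count any graded fasting result as treatment-emergent and remove these women from fasting change-from-baseline summaries.

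The true number cannot be derived from the documents. The illustration of 1-19 of 235 women per test is an upper-type figure for three reasons: it takes every woman in f as having no usable earlier value, some of these women would have worsened by a grade anyway, and parent-study values, if permitted, would shrink it.

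The effect is confined to secondary descriptive safety tables. The primary endpoint is untouched, and nothing is concluded here about the Week 48 comparison. It is still worth correcting, because the error runs in one direction and the remedy is small.

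**What to change.** In SAP 3.8.1 and 3.8.3, add a rule for fasting glucose and lipids:

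1. Baseline is the last fasting value on or before Study Day 1.
2. If there is none, baseline is the protocol's 72-hour fasting redraw, up to Study Day 4. That record is removed from the post-baseline windows and from treatment-emergent grading.
3. If there is no redraw either, the woman is left out of the numerator and denominator of the treatment-emergent summary for that test, in line with how SAP 7.2.2.1 handles nonfasting glucose.

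Also state whether parent-study fasting values may be used, and report how many women fall under rules 2 and 3. Record the departure from Protocol 8.3 and 8.6.3 in SAP 7.8.

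Separately, Protocol 6.2.2 needs reconciling. It places all procedures before dosing, requires dosing on the day of the visit, and allows the fasting draw up to 72 hours after that visit.

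The cost is a few lines of SAP text and minor programming. The downside is that a few baselines will follow one to three doses of study drug. Rule 3 used alone would avoid that, but it would not restore the change-from-baseline data.

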3.8.2. Analysis Windows

Subject visits might not occur on protocol-specified days. Therefore, for the purpose of analysis, observations will be assigned to analysis window. Since the final analysis only includes the all B/F/TAF analysis, only data included in the all B/F/TAF analysis will be assigned analysis windows.

For data listings, the observations collected from the randomized phase of the study for the subjects who were randomized to SBR group will not have analysis window assigned and will be included in listings with derived visit as blank.

The analysis windows for HIV-1 RNA, CD4+ cell count, CD4 %, hematology, chemistry, urinalysis, urine pregnancy laboratory tests, eGFR_{CG}, vital signs, and weight are presented in [Table 3-1](#).

Table 3-1. Analysis Windows for HIV-1 RNA, CD4+ cell count, CD4 %, Hematology, Chemistry, Urinalysis, and Urine Pregnancy Laboratory Tests, eGFR_{CG}, Vital Signs, and Weight

Visit ID	B/F/TAF			SBR to B/F/TAF		
	Nominal Day	Lower Limit	Upper Limit	Nominal Day	Lower Limit	Upper Limit
Baseline			1			1
Week 4	28	2	42			
Week 8	56	43	70			
Week 12	84	71	126	84	2	126
Week 24	168	127	210	168	127	210
Week 36	252	211	294	252	211	294
Week 48	336	295	378	336	295	378
Week 60	420	379	462	420	379	462
Week 72	504	463	546	504	463	546
Week 84	588	547	630	588	547	630
Week 96	672	631	714	672	631	714
Week k	k*7	(k-6)*7+1	(k+6)*7	k*7	(k-6)*7+1	(k+6)*7

The analysis windows for metabolic assessments (including fasting glucose and lipid panel: total cholesterol, high density lipoprotein [HDL], direct low density lipoprotein [LDL], triglycerides, and total cholesterol to HDL ratio) are presented in [Table 3-2](#).

Table 3-2. Analysis Windows for Metabolic Assessments

Visit ID	B/F/TAF			SBR to B/F/TAF		
	Nominal Day	Lower Limit	Upper Limit	Nominal Day	Lower Limit	Upper Limit
Baseline			1			1
Week 12	84	2	126			
Week 24	168	127	252	168	2	252
Week 48	336	253	420	336	253	420
Week 72	504	421	588	504	421	588
Week 96	672	589	756	672	589	756
Week k	k*7	(k-12)*7+1	(k+12)*7	k*7	(k-12)*7+1	(k+12)*7

The analysis windows for thyroid stimulating hormone (TSH; thyrotropin) and renal function (including urine albumin, urine creatinine, urine RBP, and urine beta-2 microglobulin, and derived ratios assessments) are presented in [Table 3-3](#).

Table 3-3. Analysis Windows for TSH, Renal Function, and HCV RNA Assessments

Visit ID	Nominal Day	Lower Limit	Upper Limit
Baseline			1
Week 24	168	2	252
Week 48	336	253	420
Week 72	504	421	588
Week 96	672	589	756
Week k	k*7	(k-12)*7+1	(k+12)*7

The analysis windows for ECG assessments are presented in [Table 3-4](#).

Table 3-4. Analysis Windows for ECG Assessments

Visit ID	Nominal Day	Lower Limit	Upper Limit
Baseline			1
Week 24	168	2	252
Week 48	336	253	504
Week 96	672	505	756
Week k	k*7	(k-12)*7+1	(k+12)*7

3.8.3. Selection of Data in the Event of Multiple Records in an Analysis Window

Depending on the statistical analysis method, single values are required for each analysis window. For example, change from baseline by visit usually requires a single value, whereas a time to event analysis would not require one value per analysis window. When a single value is needed, the following rule(s) will be used.

If multiple nonmissing numeric observations exist in a window, then records will be chosen as follows:

- For baseline, the latest available record on or prior to the first dose date of B/F/TAF will be selected. If there are multiple records with the same collection time or no collection time recorded on the same day, average will be used for the baseline value, except for HIV-1 RNA (see below).
- For postbaseline visits:
 - For CD4+ cell count and CD4%, the record(s) collected on the latest day in the window will be selected for analysis.
 - For other numeric observations (eg, except HIV-1 RNA, CD4+ cell count, and CD4%), the record(s) collected on the day closest to the nominal day for that visit will be selected. If there are 2 days equidistant from the nominal day, the later day will be selected.
 - For any numeric observations except HIV-1 RNA, if there are multiple records on the selected day, the arithmetic mean will be used.
- For baseline and postbaseline HIV-1 RNA, the latest (considering both collection date and time) record(s) in the window will be selected. If both “HIV RNA Taqman 2.0” and “HIV RNA Repeat” (ie, the HIV-1 RNA result obtained from an additional aliquot of the original sample) are available with the same collection time, the results from the “HIV RNA Repeat” will be selected for analysis purposes; otherwise, if there are multiple “HIV RNA Taqman 2.0” records with the same collection time, the geometric mean will be taken for analysis purposes.

If multiple valid nonmissing categorical observations exist in a window, records will be chosen as follows:

- For baseline, the last available record on or prior to the first dose date of B/F/TAF will be selected. If there are multiple records with the same collection time or no collection time recorded on the same day, the value with the lowest severity will be selected (eg, normal will be selected over abnormal for safety ECG findings).
- For postbaseline visits, the most conservative value within the window will be selected (eg, abnormal will be selected over normal for safety ECG findings).

